7.3 Data collection

7.3.1 Quantitative data

Quality assessment

In each NH, a quality assessment of the medicines' pathway will occur at baseline (i.e. before) and at the end of the study (i.e. after). This assessment will be performed through the quick scan of the two-part quality assessment instrument that has been recently developed by our research group (see Appendix 3) (16). The quick scan is based on the KAs as defined in the framework of the medicines' pathway. For this quick scan, these KAs have been adjusted for readability during the pilot study. This way, the KAs are more understandable for each member of the interdisciplinary team in the NHs. The quick scan applies the importance-performance analysis (IPA) methodology, a method that has been successfully used in healthcare to identify quality aspects with the highest priority. In such assessment, respondents are asked to score both the importance and current performance of items under assessment (i.e. KAs) (17,18). The results of this analysis can be visualized on an IPA-graph that plots performance on the x-axis and importance on the y-axis. Four quadrants are formed in this process: "Concentrate Here" (high importance, low performance), "Keep up the Good Work" (high importance, high performance), "Low Priority" (low importance, low performance), and "Possible Overkill" (low importance, high performance) (19).

The only criterion applied with regard to respondents in the quick scan, is that they need to be involved in the medicines' pathway of the NH (e.g. coordinating physician, nurses, nurse aids, pharmacist, ...). Respondents are asked to score the performance of each KA (i.e. To what degree is the KA performed as described?) using a 5-point Likert scale with response options 'Absolutely so', 'Rather so', 'A little', 'Rather not', 'Absolutely not'. Likewise, respondents are invited to score the importance of each KA (i.e. How important is it that the KA is performed as described?) by means of a 4-point Likert scale, including response options 'Very important', 'Rather important', 'Rather not important', and 'Not important'.

The quick scan is available in Limesurvey®, an online survey platform, and will be sent to the project coordinators of participating NHs. Project coordinators will be invited to complete the questionnaires themselves and to further distribute the quick scan to NH staff they consider relevant.

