7.4 Data analysis

7.4.1 Primary objective: effectiveness of different formats and intensities of support

The primary outcome measure consists of the overall performance score with regard to the medicines' pathway in participating NHs. This overall performance score will be calculated at baseline (i.e. before) and at the end of the study (i.e. after), and will be calculated on data collected with the quick scan, in particular the performance assessment. The importance assessment will thus not be used to determine the primary outcome.

For data analysis, responses collected through the performance assessment will be dichotomized. Responses 'Absolutely so' and 'Rather so' will be considered as 'key activity implemented (i.e. scored 1). The other response options ('A little', 'Rather not', 'Absolutely not') will be scored 0 and thus considered as 'not implemented'. For each respondent, a performance score will be calculated by determining the proportion of KAs considered as 'implemented'.

A before-after comparison of the overall performance scores will be executed by means of a linear, mixed model with random effects of NH and respondent (most respondents will be involved in before and after setting) and fixed effects of track, time (before/after), the interaction between track and time, type of respondent (coordinating physician, nurse, pharmacist, etc.), the NH's membership of a professional association and the number of beds available. Note that the focus of interest is the interaction between track and time. From the model, least-squares means (with 95% confidence intervals) and changes in means will be reported. If required, a transformation of the performance score will be considered to obtain a more symmetric distribution of the model residuals.

The changes of the activity-specific performance will be evaluated for each KA separately using a generalized linear mixed model (i.e. a logistic regression model with random effects of NH and respondent) with the same fixed effects as in the linear mixed model.

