8 STUDY POPULATION AND RECRUITMENT

A pilot study will be performed first, in approximately five to ten NHs. The project call (see Appendix 10 and 11) for this phase is planned to be launched in February 2024 but will not occur before receiving

approval of the Ethics Committee. A call for the actual cluster RCT, which will include approximately 100 NHs, is scheduled to be launched in March 2024. As the sample size of 100 NHs has been determined and defined in the Decision of the Flemish Government, no sample size calculation has been performed.

Project calls for NHs will be distributed by Departement Zorg (Flemish Government) and umbrella organizations (i.e. VLOZO, VVSG and Zorgnet-Icuro). In addition to this, a dedicated call will be targeted at NHs that contacted the research team during the last year with regard to the lifelong learning course 'Coordinating pharmacist in nursing homes' or to request access to materials and tools developed during earlier research projects (e.g. Come-On study, RESPECT project).

Nursing homes who are interested to participate will be asked to register through an online application form that will be made available in Qualtrics (see Appendix 12). In this application form, NHs will be asked to formulate a motivation for participation, to indicate the willingness of the coordinating physician to participate, to make a proposal for the composition of their local project team, to suggest who will be the local project coordinator, etc.

Recruitment of NHs will occur in two stages. First, if more than 100 NHs apply, a set of 100 NHs will be drawn at random from the pool of NHs who have expressed their interest to participate in the study. This sampling, if performed, will take into account the NH's membership to a professional association, meaning that the selection of NHs will occur proportionally to the real-life distribution of NH memberships in Flanders (i.e. no membership, Zorgnet-Icuro, VVSG, and VLOZO).

The sample of 100 will be randomised into the different tracks (cfr. supra), stratified on membership to a professional association, initial performance score and number of beds. Since these characteristics of all participating centres are known at the start of the study, a list can be created with all possible randomisations safeguarding the required balance in characteristics. From this list of acceptable randomisations, one will be drawn at random.

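### No rule ties the follow-up quick-scan respondents to those chosen before allocation, and a coordinator who knows the track picks them, so the track × time estimate is open to selection bias.

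*Protocol*

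**What the plan says.** Section 7.3.1 of the protocol schedules the quick scan at baseline and at the end of the study and describes one distribution procedure for both. The link goes to the coordinator: "Project coordinators will be invited to complete the questionnaires themselves" and to "further distribute the quick scan to NH staff they consider relevant". On eligibility it says: "The only criterion applied with regard to respondents in the quick scan, is that they need to be involved in the medicines' pathway". The section gives no respondent list, minimum number or separate rule for the second round.

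Section 7.4.1 states that the overall performance score "will be calculated on data collected with the quick scan, in particular the performance assessment". The score is computed per respondent, as the share of key activities rated as implemented. The model has random effects of nursing home (NH) and respondent and a fixed effect of respondent type, and the term of interest is track × time. The respondent effect is justified by the remark that "most respondents will be involved in before and after setting".

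Section 8 says randomisation is "stratified on membership to a professional association, initial performance score and number of beds".

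**The concern.** Randomising homes protects the comparison only if the people who supply the outcome are chosen without regard to the allocation. That holds at baseline, where the choice precedes allocation. It is not secured at follow-up, where the choice is made by a member of the local project team who knows what support the home received.

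More intensive support could bring more staff into the improvement work, and a coordinator could naturally regard those staff as the relevant people to ask at the end. If they rate more favourably than the people they displace, the track × time estimate contains a change in who answers as well as any change in the medicines' pathway.

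Track 4 has a specific route. Under section 7.2.4 the coordinating pharmacist joins the care team and leads the initiatives. Section 7.3.1 names pharmacists among the possible respondents, and nothing excludes this person from rating their own work at follow-up.

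**Working it through.** **Timing and knowledge of track**
- The initial performance score must exist before homes are randomised (section 8), so baseline respondents are chosen without knowledge of the track.
- The end-of-study scan follows a year of overt support. In Tracks 2 to 4 every home hosts at least one intervision meeting, and the coordinators of hosting homes are invited to a preparatory session organised per arm (section 7.2.2). The protocol does not discuss blinding, but the coordinator's knowledge of the track follows from the design.
- The overlap of respondents is stated as an expectation in section 7.4.1. The procedure in section 7.3.1 contains nothing that produces it.

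**What the model absorbs**
- The respondent effect controls for a person's general rating level only where that person is measured twice.
- The respondent-type effect corrects for a shift in professional mix, not for choosing more engaged people within a profession.

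**Size (illustration)**

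The protocol gives no SD, effect size or sample size calculation, so there is no figure to reproduce and every input here is an assumption: 25 NHs per track (100 homes over four tracks); m = 8 respondents per NH at each time; u = 2 replaced at follow-up in one track only, leaving k = 6 who answer twice; replacements score δ = 10 or 20 points higher on a 0–100 scale (10 points is 0.10 × 29 = 2.9 key activities); no true effect. Let σ² be the within-NH variance, ρ the share of it due to the respondent, and ν the SD of an NH × time deviation.

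*Respondents linked, as the model intends.* Generalised least squares weights the 6 paired changes against the unpaired contrast between 2 newcomers and 2 leavers. The weight on the unpaired part is

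w = u(1−ρ) / [k + u(1−ρ)], and bias = wδ.

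SE² = 2σ²(1−ρ) / {25[k + u(1−ρ)]} + 2σ²(1−ρ) / (25 × 8) + 4ν²/25.

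- Case A, respondent SD 12 and residual SD 10: σ² = 144 + 100 = 244 (SD 15.6), 1−ρ = 100/244 = 0.410, w = 0.820/6.820 = 0.120. Bias = 1.2 or 2.4 points.
  - ν = 0: SE = √(1.173 + 1.000) = 1.47, so 0.8 or 1.6 SE.
  - ν = 5: SE = √(2.173 + 4) = 2.48, so 0.5 or 1.0 SE.
- Case B, σ = 20 and ρ = 0.5: w = 1/7 = 0.143. Bias = 1.4 or 2.9 points.
  - ν = 0: SE = √(2.286 + 2.000) = 2.07, so 0.7 or 1.4 SE.
  - ν = 5: SE = √(4.286 + 4) = 2.88, so 0.5 or 1.0 SE.

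A direct least-squares calculation that also included an NH random effect gave the same values. With q the bias in SE, a nominal 5% two-sided test rejects with probability 1 − Φ(1.96 − q) + Φ(−1.96 − q): about 8% at q = 0.5 and 36% at q = 1.6.

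*Respondents not linked.* The bias is the raw shift in the home mean, δu/m = 10 × 2/8 = 2.5 or 20 × 2/8 = 5.0 points. With ν = 0, SE = √(4σ²/200), which is 2.21 for σ² = 244 and 2.83 for σ² = 400.

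*Same people re-surveyed.* u = 0, so w = 0 and the selection bias is zero.

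**The case against.** **The scenario is one-sided.** It assumes replacement in one track only, and by more favourable raters. Every track has a local project team of at least three that may involve other staff (section 8), and engaged staff might rate more severely once they know what good practice looks like. This stands. The documents support neither a direction nor a rate of replacement, so a reader who infers that the estimate will be biased towards the better-supported tracks goes beyond them.

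**The mixed model handles it.** It does so in part. The raw shift of 2.5 to 5 points is not the bias under the planned model with linked respondents, which is roughly half of that. A reader who takes the raw shift as the size of the problem ignores the respondent effect.

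**Forwarding a survey link means the two questionnaires cannot be matched.** This is a tempting inference but it is not established. The authors plan a respondent effect, so they intend to match. The quick scan and its consent text are in appendices that are not shown and may contain a personal code. All that can be said is that the protocol text does not describe the link.

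**Section 8 sets a recruitment target.** It aims for the project team plus five other staff per home. That is a general recruitment aim covering those involved in or affected by the project. It does not say who answers the quick scan or that the same people answer twice.

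**This belongs in the statistical analysis plan.** The analysis set may be defined there. Who receives the questionnaire is data collection, which section 7.3.1 already fixes, and analysis cannot recreate a fixed cohort afterwards.

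**Conclusion.** The concern holds as a weakness in the stated procedure. Someone who knows the allocation has discretion over who supplies the primary outcome after randomisation, and the expected overlap of respondents rests on no rule. The procedure allows track-dependent selection bias in the track × time estimate. It does not show that such bias will occur.

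Under the planned model with linked respondents, the illustration gives about 1.2 to 2.9 points, or 0.5 to 1.6 standard errors. If the two questionnaires could not be matched it would be 2.5 to 5 points. These sizes depend entirely on the assumed replacement, rater shift and variance components. The conclusion does not, because it follows from reading sections 7.3.1, 7.4.1 and 8 together. Self-rating by staff who know their track would remain as a separate measurement issue even after the fix.

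**What to change.** In section 7.3.1:
- Fix a coded respondent list by role for each home before allocation is disclosed. Where baseline is already complete, use the baseline respondents.
- Have the research team send individual Limesurvey invitations with a persistent code to that list at both times. This also documents the link that the respondent effect needs.
- Replace leavers by a fixed same-role rule.

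Base the primary score on that list. Exclude the Track 3 coach and the Track 4 coordinating pharmacist at both times; under sections 7.2.3 and 7.2.4 either may already supply the home and so be eligible to respond. Use later additions only in a sensitivity analysis.

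The cost is modest coordination across about 100 homes. The lists should be coded rather than openly named, because staff are rating their own employer and section 9.2 promises coded data. Neither the instrument nor the number of measurements changes.

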7.3.2 Qualitative data

Interviews and focus groups

Throughout the POOMAH study, semi-structured interviews and focus groups will be performed with members of local project teams (see '7. Study population and recruitment'), as well as with other NH staff, NHRs and relatives involved in quality assessment of the medicines' pathway or in setting up and monitoring of quality improvement initiatives. These interviews/focus groups will be organized during working hours, at the NH and at a time that fits participants' availabilities, and will last 30 minutes to one hour.

Intervision meetings with NHs will be considered as focus groups and will be included in the qualitative data analysis (see '7.2.2 Intervision'). Intervision meetings will be organized during working hours, and will last approximately one to two hours.

Likewise, the bimonthly intervision meetings with external coaches (i.e. Track 3) and coordinating pharmacists (i.e. Track 4), will be considered as focus groups.

All interviews and focus groups, including intervision meetings, will be performed by members of the research team: AF, AD, and/or VF. Preliminary topic guides for interviews and focus groups are shown in Appendix 8. Interviews and focus groups will be audio-recorded to facilitate data analysis.

Documentation

Nursing homes will be instructed to deliver all documentation related to the quality improvement project (i.e. performing the quality assessment, setting up and monitoring of quality improvement initiatives). The local project coordinator will collect all documents and will provide these to the research team via KU Leuven OneDrive in a pseudonymized manner (cfr. supra).

Tasks performed by external coaches and coordinating pharmacists

External coaches and coordinating pharmacists will be asked to register their activities throughout the study. The pharmacists will complete a shared registration form in Excel via KU Leuven OneDrive. In these forms, they will be asked to record the date of the visit, the duration of each visit and the activities performed during these visits.

7.4 Data analysis

7.4.1 Primary objective: effectiveness of different formats and intensities of support

The primary outcome measure consists of the overall performance score with regard to the medicines' pathway in participating NHs. This overall performance score will be calculated at baseline (i.e. before) and at the end of the study (i.e. after), and will be calculated on data collected with the quick scan, in particular the performance assessment. The importance assessment will thus not be used to determine the primary outcome.

For data analysis, responses collected through the performance assessment will be dichotomized. Responses 'Absolutely so' and 'Rather so' will be considered as 'key activity implemented (i.e. scored 1). The other response options ('A little', 'Rather not', 'Absolutely not') will be scored 0 and thus considered as 'not implemented'. For each respondent, a performance score will be calculated by determining the proportion of KAs considered as 'implemented'.

A before-after comparison of the overall performance scores will be executed by means of a linear, mixed model with random effects of NH and respondent (most respondents will be involved in before and after setting) and fixed effects of track, time (before/after), the interaction between track and time, type of respondent (coordinating physician, nurse, pharmacist, etc.), the NH's membership of a professional association and the number of beds available. Note that the focus of interest is the interaction between track and time. From the model, least-squares means (with 95% confidence intervals) and changes in means will be reported. If required, a transformation of the performance score will be considered to obtain a more symmetric distribution of the model residuals.

The changes of the activity-specific performance will be evaluated for each KA separately using a generalized linear mixed model (i.e. a logistic regression model with random effects of NH and respondent) with the same fixed effects as in the linear mixed model.

For the process-specific performance (which consists of a sum over a set of KAs), the same approach as for the overall performance score will be followed. However, since for some processes the number of KAs is small, an alternative approach will be considered, i.e. an analysis on KA level using the generalized linear mixed model modeling the binary outcome (Yes/No) on KA level with an additional random effect capturing the correlation between the multiple KAs per respondent at the same timepoint¹.

¹ Note that this alternative approach can also be considered for the overall performance score, i.e. modeling simultaneously the 29 binary KAs, instead of modeling the sum (using a logistic regression model with random effects of NH, respondent and respondent nested within a timepoint). The advantage is that no distributional assumption is required for the score obtained by summing the KAs. However, computational issues might arise, requiring a simplification of the random effects structure.

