6 OUTCOMES

6.1 Primary outcomes

The primary outcome consists of the quality of the medicines' pathway in participating NHs, represented by overall performance scores, measured at the end of the study (i.e. 1 year).

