7.2.4 Integration of a coordinating pharmacist

A coordinating pharmacist will be integrated in the care team of each NH assigned to Track 4. The pharmacist will be present for 78 hours, spread over the whole intervention year. Coordinating pharmacists will become members of the interprofessional team present in each NH, i.e. they do not remain independent. The coordinating pharmacist leads the development and implementation of initiatives to improve the quality of the NH's medicines' pathway. He/she can therefor perform observations of the medicines-related processes in the NH, have in-dept discussions with HCPs active in the NH (including general practitioners),... Additionally, the coordinating pharmacist, as an active member of the care team, can talk with residents about medication, perform medication reviews, give training to nurses and care aids, participate in interprofessional discussions on a NHRs care plan,... Coordinating pharmacists will have completed the lifelong learning course 'Coordinating pharmacist in nursing homes' (15), and will on their turn be supervised by the research team. Some of these pharmacists are already involved in supplying medication to NHs. If so, these pharmacists will be assigned to a NH they currently supply, provided it is geographically feasible. If no NH they supply is selected for the study in track 4, or if no match can be made, these pharmacists can be assigned a role as coordinating pharmacist to a NH that they do not deliver, based on geographical accessibility. Pharmacists who are not involved in supplying NHs, will be assigned to NHs based on geographical accessibility. This approach ensures that both pharmacists who currently supply NHs and those who do not, are recruited, allowing for an exploration of both perspectives during the quality assessment of this study.

An agreement between KU Leuven and each coordinating pharmacist will be made up for the duration of the POOMAH study. This agreement includes a deontological clause which states that in carrying out the project, the deontological rules must be respected, and activities (actions) intended to promote or that could be interpreted as an attempt to promote their own pharmacy (or pharmacy group) must be avoided.

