7.4.2 Secondary objectives

Number of (psychoactive) medications used by NHRs

The number of (psychoactive) medications used by NHRs will be considered as a key secondary outcome. These data will be collected at the beginning of the intervention and after the intervention and will be collected through the monitoring tool that has been developed by VAD.

A before-after comparison of the number of (psychoactive) medications will be executed by appropriate statistical methods.

Baseline quality of the medicines' pathway and Benchmark

Using the baseline data, descriptive statistics will be reported based on the proportion of respondents that indicated a KA is performed 'Rather so' and 'Absolutely so'. Descriptives will refer to overall performance score (sum over 29 KAs), process-specific performance (sum over set of KAs) and activity-specific performance (each KA separately). For benchmarking purposes, linear and generalized linear mixed models will be used on the baseline data yielding Empirical Bayes (EB) estimates for the NH-specific levels. These EB estimates "correct" for the difference between the number of respondents per center and for differences with respect to the fixed factors included in the model (type of respondent, membership of a professional association and the number of beds available). The linear model(s) will contain a random effect of NH and the generalized linear models (fitted on multiple KAs simultaneously) will additionally include a random effect of respondent (the latter to take into account the correlation between the KAs within the same respondent).

Associations between organizational characteristics and quality of the medicines' pathway

In a set of exploratory analyses, the aforementioned (generalized) linear mixed models planned for benchmarking will be extended to determine potential associations between organizational characteristics (see Appendix 9) and the quality of the medicines' pathway in NHs.

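### The primary track-by-time estimate weights each nursing home roughly by its number of respondents, although the outcome describes homes and homes are randomised

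*Protocol*

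**What the plan says.** Section 6.1 places the outcome at home level: "The primary outcome consists of the quality of the medicines' pathway in participating NHs, represented by overall performance scores". Section 8 randomises homes to the four tracks.

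Section 7.4.1 works at respondent level: "For each respondent, a performance score will be calculated by determining the proportion of KAs considered as" implemented. The scores are analysed with a "linear, mixed model with random effects of NH and respondent", with track, time, their interaction, respondent type, association membership and beds as fixed effects. The target is explicit: "Note that the focus of interest is the interaction between track and time". The footnoted alternative, which models all 29 activities jointly, adds an effect for respondent within time point but nothing for home by time. No step aggregates or reweights to home level.

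On respondent numbers, section 7.3.1 asks coordinators to complete the scan and to "further distribute the quick scan to NH staff they consider relevant". Involvement in the pathway is the only condition; no minimum, maximum or quota is set. Section 8 aims for about 15 participants per home, including residents and relatives, of whom at least 3 are project-team members and five are other staff. This is a recruitment aim for the whole project, not a quota for the quick scan.

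Unequal respondent numbers are addressed once, in section 7.4.2, where the baseline benchmarking uses Empirical Bayes estimates that allow for them.

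**The concern.** Respondents act here as raters of their home. A home with 30 raters is not six times as important as a home with five when the question is which support improves the pathway in participating homes. A random home effect is usually expected to moderate such imbalance. It does so for score levels, but not for change over time, and change is the primary contrast.

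Section 7.1 expects the improvement initiatives to differ between homes, so the changes probably differ too. Once they do, the weights matter. They set which average of home effects is reported if change and respondent number are related, and they affect precision even if these are unrelated.

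**Working it through.** The protocol gives no sample size calculation, effect size, variance or respondent number, so there is no figure of the plan to reproduce. All respondent numbers, gains and variance shares below are assumptions.

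**Weights under the stated model.** For respondent j in home i at time k, the score is fixed effects + u(i) + r(ij) + e(ijk). For a respondent seen twice, u and r cancel from the change, as do respondent type, membership and beds, which enter without a time interaction. What remains is the track's change plus a difference of two residuals, with variance 2σ². Home i's mean change has model variance 2σ²/n(i), so its weight is n(i)/Σn.

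**Check with exact generalised least-squares weights.** Assume 25 homes in a track (100 homes, four equal tracks): 22 with 8 respondents and 3 with 40.

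- Stated model: the 3 homes carry 120/(120 + 176) = 40.5% of the track's change, against 3/25 = 12% under equal weights. This holds at a home-level intraclass correlation of 0.10 and of 0.20, and with 100%, 75% or 50% of respondents paired.
- Baseline level: their weight is 29.0% (correlation 0.10) or 27.7% (0.20). The random home effect softens levels, not change.
- With a random home-by-time variance τ² added, the weight is proportional to 1/(2τ² + 2σ²/n). With τ² at 2%, 5% or 10% of total variance and σ² at 50%, full pairing, their weight is 25.7%, 19.7% or 16.5%.

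**Effect on one track's estimate.** Assume 8, 9 and 8 homes with small, middle and large respondent numbers, and true gains of 8, 6 and 3 points. The home average is (8×8 + 9×6 + 8×3)/25 = 142/25 = 5.68.

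| Respondents | Planned estimate | Against 5.68 | Effective homes (Σn)²/Σn² |
|---|---|---|---|
| 6/8/12 | (384 + 432 + 288)/216 = 5.11 | 10% below | 216²/2016 = 23.1 |
| 5/10/30 | (320 + 540 + 720)/370 = 4.27 | 25% below | 370²/8300 = 16.5 |

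**Direction.** Reverse the gains to 3, 6 and 8, and the home average stays 5.68. The estimates become (144 + 432 + 768)/216 = 6.22 and (120 + 540 + 1920)/370 = 6.97, about 10% and 23% above.

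**Contrast between tracks.** If a comparator track has the same respondent numbers and every home there gains 2 points less, the planned contrast is 4.27 − 2.27 = 2.00, the same as the home-average contrast. A shared gradient cancels; only a gradient that differs between tracks shifts the result.

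**Precision when change is unrelated to respondent number.** The estimate's variance has two parts.

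- Between homes: 2τ²/(effective homes). Against equal weights, the planned weights inflate this part by 25/23.1 = 1.08 or 25/16.5 = 1.52.
- Respondent noise: 2σ²/Σn under the planned weights, the minimum. Under equal weights it is 2σ²·Σ(1/n)/25². For 6/8/12 the ratio is (3.125/625)×216 = 1.08; for 5/10/30 it is (2.767/625)×370 = 1.64.

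The planned weights therefore lose precision only to the extent that τ² is above zero. If τ² is zero they are the most precise choice.

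**The case against.** The strongest case against is that the plan nowhere promises equal weight per home, that a respondent-level mixed model is a common analysis for a cluster trial, and that weighting and sensitivity analyses may stand in a statistical analysis plan that is not at hand. This stands in part: nothing in 7.4.1 contradicts itself here. But 7.4.1 does fix the model and its footnoted alternative, and both imply respondent weighting for an outcome that 6.1 attributes to homes.

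The sizes are assumed throughout, and this stands. The only guide is the section 8 aim of 3 + 5 = 8 staff, the same for every home. It points nearer to 6/8/12 than to 5/10/30, though it does not bind the quick scan.

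Strict equal weighting is also debatable, because a home with two raters would count as much as one with 30. That is a reason to allow a random home-by-time effect as one solution; it moves the weights part of the way.

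Two stronger readings are tempting.

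- A reader might infer that large homes pull the result down because support is a fixed number of hours per home; for Track 4, "The pharmacist will be present for 78 hours, spread over the whole intervention year". The documents do not support this. Fixed pharmacist hours apply only to Tracks 3 and 4, and nothing links beds to respondent numbers or hours per bed to the score. Keen homes with many respondents could push the other way.
- A reader might infer that the baseline description in 7.4.2 has the same flaw, since "descriptive statistics will be reported based on the proportion of respondents that indicated a KA is performed" as described. The text does not say that respondents are pooled across homes, so this is not part of the point.

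**Conclusion.** The concern holds in a conditional form. That the weights in the track-by-time estimate follow respondent numbers is a property of the stated model: exact for fully paired respondents, and close to it in the partly paired cases checked. Whether this shifts the result depends on the spread of respondent numbers and on whether change is related to them; the protocol gives neither. On the assumed gains, one track's estimate lies about 10% (6/8/12) to 25% (5/10/30) from the home average, in either direction. The shift is smaller in the between-track contrast if tracks share the gradient, and zero if change is unrelated to respondent number. In that last case the loss is one of precision, and only to the extent that homes differ in change.

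It would be too strong to say that a few homes will decide the result: with equal respondent numbers there is no imbalance. Stratifying on beds does not remove the risk, because it does not balance response numbers, and the number answering at the end is known only after allocation.

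**What to change.** In section 7.4.1:

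1. State that the target is the average effect over participating homes.
2. Choose one of two analyses. Either compare tracks on home-level mean scores, adjusted for baseline and respondent mix; or add a random home-by-time effect to the primary model and to its footnoted alternative, with the home-level analysis as a prespecified sensitivity analysis.
3. Report the number of respondents per home and time point, by track.

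This needs no new data, only wording, and should be settled before outcome data are seen. The cost is somewhat wider intervals where respondent noise dominates. In the limit of equal weights, full pairing and no difference in change between homes, the factor is √1.08 = 1.04 for 6/8/12 respondents and √1.64 = 1.28 for 5/10/30. The random home-by-time effect costs less in that situation, because its weights stay close to respondent numbers when the estimated home-by-time variance is small.
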